2.3.2 Secondary Endpoints

2.3.2.1 Safety endpoints

Criteria for assessing long term safety of GH treatment focusing on the secondary objectives are:

- **Immunogenicity:** Number and percentage of patients developing anti-rhGH antibodies through the follow-up period after end of GH treatment is the secondary safety endpoint associated with monitoring and assessing immunogenicity.

Patients will be screened for anti-rhGH antibodies at baseline and 6 months after the end of treatment. Only in case of positive antibodies measurements in previous visit follow-up measurements are planned after 1 year, 5 years and 10 years. Positive antibodies are defined as values above 1.76. Unscheduled visits will be excluded from the analysis.

- **Laboratory evaluations – safety parameters:** Change from baseline (Shift from baseline, as applicable) at 6 months, 1 year, 5 years and 10 years after end of GH treatment in laboratory safety parameters as follows:
 - **Hematology:** Hemoglobin, hematocrit, white blood cell count (WBC, total and differential), red blood cell count (RBC), platelet count, mean cell volume (MCV), mean cell hemoglobin (MCH), mean cell hemoglobin concentration (MCHC), erythrocyte sedimentation rate (ESR).
 - **Biochemistry:** Creatinine, urea, aspartate aminotransferase (AST), alanine aminotransferase (ALT), gamma-glutamyltransferase (gamma-GT), alkaline phosphatase, total bilirubin, albumin, total protein, HDL, LDL, sodium, potassium, chloride, uric acid, fasting total cholesterol, fasting triglycerides, calcium, phosphorus.
 - **Thyroid function:** Free thyroxine and thyroid stimulating hormone.
 - **Urinalysis:** pH, glucose, ketones, bilirubin, protein.

- Number and percentage of patients with Adverse Events and Serious Adverse Events
- Change from baseline in vital signs parameters (blood pressure, pulse rate) and body weight, BMI, and BMI SDS will be assessed at each visit (baseline, 6 months, 1, 5, and 10 years after termination of treatment). BMI is calculated by [weight in kg] divided by [height in m]². For further details on the calculation of BMI SDS, see Section 5.1.
- Number and percentage of patients with significant finding in any body systems: head (external), eyes, ears, nose and throat, lungs, cardiovascular system, abdomen, musculo-skeletal system, skin, lymph nodes, central nervous system, and where appropriate, others. Physical examinations are performed at baseline, 6 months, 1 year, 5 and 10 years after end of treatment.

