4.7 Analysis of secondary endpoints

4.7.1 Safety evaluations

4.7.1.1 Immunogenicity

The number and percentage of patients with positive anti-rhGH antibodies (ABs) will be tabulated by visit. For patients with positive anti-rhGH results, all results of anti-rhGH testing will be listed by center, patient number, and visit and will include: parameter, value, unit (if available), and assessment if positive or negative

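### Excluding unscheduled visits from the antibody analysis can leave out a patient whose only positive after baseline was found at such a visit, although the endpoint covers the whole follow-up

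*SAP*

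**What the plan says.** SAP section 2.3.2.1 gives the endpoint as "Number and percentage of patients developing anti-rhGH antibodies through the follow-up period after end of GH treatment is the secondary safety endpoint" for immunogenicity.

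The same item sets the sampling: "Patients will be screened for anti-rhGH antibodies at baseline and 6 months after the end of treatment". After that, testing is conditional: "Only in case of positive antibodies measurements in previous visit follow-up measurements are planned after 1 year, 5 years and 10 years". The cut-off follows ("Positive antibodies are defined as values above 1.76"), and then the exclusion: "Unscheduled visits will be excluded from the analysis". No exception is made for a positive result.

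Section 4.7.1.1 gives the planned output: "The number and percentage of patients with positive anti-rhGH antibodies (ABs) will be tabulated by visit". It adds a listing: "For patients with positive anti-rhGH results, all results of anti-rhGH testing will be listed by center, patient number, and visit". Neither sentence mentions unscheduled results, and no count of patients ever positive after baseline is planned.

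Section 4.1 separately limits all by-visit analyses to the CRF visits F1 to F4, with F4 shown as the termination visit.

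**The concern.** The endpoint asks whether a patient developed antibodies at any time in the follow-up. The exclusion works at the level of visits. The two fit together for a by-visit table, but not for a per-patient count over the whole period.

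For the by-visit table the exclusion adds little, because section 4.1 already restricts such tables to F1 to F4. Its additional effect falls on the follow-up-wide count, where it can remove a positive result that was actually observed.

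The introduction to the SAP names immunogenicity as one of two particular safety questions behind the study. A rule that can drop an observed positive from that endpoint needs a reason, and the SAP gives none.

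**Working it through.** The SAP states no antibody rate, sample size or number of unscheduled samples, so there is no plan figure to reproduce. The check is of direction, followed by an illustration on assumed values.

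**1. Planned testing (section 2.3.2.1).** Everyone is tested at baseline and month 6. Tests at 1, 5 and 10 years follow only if the previous visit was positive. A patient negative at month 6 therefore has no planned test for the rest of the intended follow-up: 120 − 6 = 114 months, and 114/120 = 95%. This uses the planned 10 years. The study was terminated early (sections 2.1 and 4.9), so the time actually observed may be shorter.

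**2. Direction of the count.** Take results (positive or negative) at baseline, month 6, and 1, 5 and 10 years, plus two unscheduled samples, one before and one after month 6. This gives 2^7 = 128 patterns. Apply the conditional sampling rule and compare positive status after baseline with and without the unscheduled samples.

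- Month 6 positive (64 patterns): the patient is already counted, so nothing changes.
- Month 6 negative (64 patterns): no later planned sample. Of the four combinations of the two unscheduled samples, three contain a positive: 64 × 3/4 = 48 patterns where the patient is lost, and 16 unchanged.

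In total the exclusion loses the patient in 48 patterns, changes nothing in 64 + 16 = 80, and adds a patient in none. These are logical possibilities and not probabilities. A patient with no month-6 result and a positive sample recorded as unscheduled would be lost in the same way.

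**3. Direction of the percentage.** Section 2.1 routinely bases percentages on non-missing data, so the rule can also change the denominator. Assume 90 patients with a scheduled result, 3 of them positive, and 10 more whose only sample was unscheduled:

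- scheduled only: 3/90 = 3.3%
- all ten extra samples negative: 3/100 = 3.0%
- one of the ten positive: 4/100 = 4.0%

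The exclusion can thus raise or lower the percentage.

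**4. Size, on assumed values and a fixed denominator.** Let p be the share positive at scheduled visits, and q the share of the remaining patients positive only at an unscheduled visit. The share with all samples is p + (1 − p)q, and the relative shortfall is 1 − p/[p + (1 − p)q].

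| p | q | All samples | Relative shortfall |
|---|---|---|---|
| 1% to 5% | 0% | p | 0% |
| 1% | 2% | 0.01 + 0.99 × 0.02 = 2.98% | 66% |
| 3% | 1% | 0.03 + 0.97 × 0.01 = 3.97% | 24% |
| 5% | 2% | 0.05 + 0.95 × 0.02 = 6.9% | 28% |

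In whole patients, 3 of 100 against 4 of 100 means that 1 of 4 positives (25%) is missed. All of these depend on the assumed p and q.

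**The case against.** The case for leaving the rule alone has several good parts.

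- **The rule removes visits, not samples.** An extra antibody sample taken at F2, F3 or F4 belongs to a scheduled visit and stays in. Section 2.1 says all patients were called in for a last visit. The SAP does not say whether antibodies were measured then, but a result recorded under F4 would be kept. This stands: an unscheduled visit is not the only way a later positive could be seen.
- **Visits follow the CRF label.** Section 4.1 sets no date windows, and section 4.3 treats departures from the schedule as protocol deviations. A late month-6 sample entered on the F1 page would be kept. This stands too: a make-up sample is lost only if the site recorded it as unscheduled.
- **Scheduled-only analysis is conventional.** The objective in section 2.2 concerns month 6, and section 4.7.1.1 plans a table by visit. For both, the restriction is defensible and avoids uneven ascertainment. But the endpoint in section 2.3.2.1 is wider than either, and the rule is stated there without limit.
- **The listing may show such results.** It is not confined to scheduled visits. It is unclear whether a patient positive only at an unscheduled visit would qualify, and a listing does not correct the number and percentage.

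A reader might infer that the antibody result is biased low, or more favourable than the data. The SAP does not support that. It does not show that unscheduled antibody samples exist or why they would be taken, patients who are also positive at a scheduled visit are still counted, and the percentage can move in either direction.

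**Conclusion.** The point holds as a mismatch between the endpoint and the exclusion rule. A patient whose only positive after baseline was recorded at an unscheduled visit is left out of an endpoint defined over the whole follow-up, and no other part of the SAP restores that patient.

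If such samples exist, the number of positive patients can only be lowered or left unchanged. Nothing certain can be said about the direction of the percentage. The size cannot be derived from the SAP and is zero if there are no unscheduled samples; the percentages shown illustrate assumed inputs only.

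This is a low-cost improvement to a descriptive secondary endpoint. Conditional sampling after month 6 is a separate, and probably larger, reason why later positives may go unseen, and this change does not cure it.

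**What to change.** 1. In section 2.3.2.1, limit the exclusion of unscheduled visits to the by-visit table of section 4.7.1.1.
2. In section 4.7.1.1, add a patient-level row: patients with any post-baseline value above 1.76, from scheduled or unscheduled samples. Show it beside the scheduled-only count and state the denominator of each. Show patients already positive at baseline separately, since the endpoint concerns patients who develop antibodies.
3. State that the listing includes patients positive only at an unscheduled visit, with those results flagged.

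The cost is a few sentences and a small addition to one table, using data already collected. There is one small downside: patients with extra samples have more chances to test positive. The side-by-side counts make this visible.

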2.3.2.2 Efficacy Endpoints

Secondary efficacy endpoints of this study include:

- **Pharmacodynamic endpoints** Change from baseline in hGH-induced serum IGF-I and serum IGFBP-3 levels, as well as the respective serum IGF-I level SDS and serum IGFBP-3 level SDS, at 6 months, 1, 5 and 10 years after the end of treatment. For further details on the calculation/derivation of the serum IGF-I level SDS and the serum IGFBP-3 level SDS, see Section 5.3.
- **Height measurement related endpoints** include height, height SDS, final height, and final height SDS. Height will be measured according to the usual clinical practice at all visits including baseline, 6 months, 1, 5, and 10 years after the end of treatment. Height SDS will be calculated/derived from the height measurement for all visits including baseline, 6 months, 1, 5, and 10 years after the end of treatment. For further details on the calculation/derivation of height SDS, see Section 5.2. The final height is defined as the respective maximum value of height. Final height SDS is the respective SDS value for maximum value of height. For further details on the calculation/derivation of final height and final height SDS, Section 5.2.

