4.1 General considerations

Data transfer from EP00-401

Some information for analyses planned in the protocol is not provided in the CRF of this follow-up study, but in the CRF of study EP00-401 only. Therefore, the following variables provided in the CRF of EP00-401 will be transferred to this study:

- age at final visit
- gender and race
- physical examination and pubertal status at final visit
- height, height Standard Deviation Score (SDS) at final visit
- weight and BMI, BMI SDS at final visit
- fasting plasma glucose, OGTT results, fasting plasma insulin, HbA_{1C} at final visit
- IGF-I, IGFBP-3, IGF-1 SDS, and IGFBP-3 SDS at final visit
- anti-rhGH antibody testing at final visit
- safety lab at final visit
- blood pressure and pulse at final visit
- exposure to study drug

Data of study EP00-401 will be transferred to EP00-402 on the same date the EP00-402 database is locked. In general, analysis data (i.e. data created for the analysis of EP00-401) will be transferred not the original CRF data.

Study days, baseline and visits

Study days are defined as date of assessment minus date of baseline visit.

Baseline is defined as final visit of study EP00-401. If no date of final visit is available, the date of F0 baseline visit of study EP00-402 will be used instead.

Analyses by visits will be based on CRF visits, i.e. F1 Month 6, F2 1 Year, F3 5 Years, and F4 10 Years/Final. The CRF visit F4 10 Years/Final will be presented as EOS (termination visit).

Conversion factors for laboratory parameters

In order to harmonize laboratory results by using the same units, some laboratory results will be converted. Corresponding conversion factors will be listed by parameter and will provide CRF unit, SI unit and conversion factor. If albumin is given in %, the respective values will be converted to g/l using total protein values.

[figure not shown]

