4.7.2.2 Height measurements

The effect of treatment on height and height SDS will be evaluated by presenting absolute values for the observed values of height and height SDS at each visit. The effect of treatment on final height and final height SDS will be evaluated by presenting descriptive statistics for absolute values as well as absolute and relative changes from baseline of final height and final height SDS. The descriptive statistics for final height and final height SDS will only be calculated for the following patients:

- patients who completed study EP00-401
- females who discontinued study EP00-401 prematurely and are at least 16 years old when assessing final height
- males who discontinued study EP00-401 prematurely and are at least 18 years old when assessing final height.

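### Final height is defined as the maximum recorded height, which biases its change from baseline upward, the more so with more visits once growth has stopped

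*SAP*

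**What the plan says.** Section 2.3.2.2 first sets the measurement schedule: "Height will be measured according to the usual clinical practice at all visits including baseline, 6 months, 1, 5, and 10 years" after treatment ends. It then defines the endpoint: "The final height is defined as the respective maximum value of height". For the standardised version, "Final height SDS is the respective SDS value for maximum value of height". It refers to section 5.2 for detail, but on final height that section adds only that the SDS uses national reference values for age 18 or older.

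Section 4.1 fixes the comparison point: "Baseline is defined as final visit of study EP00-401". Section 4.7.2.2 then presents, as the effect of treatment, "descriptive statistics for absolute values as well as absolute and relative changes from baseline of final height and final height SDS". Patients who completed EP00-401 enter this summary without an age condition. Those who discontinued it enter subject to an age limit, for example "females who discontinued study EP00-401 prematurely and are at least 16 years old when assessing final height"; for males the limit is 18 years.

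Section 2.2 lists final height during follow-up as a secondary objective. Section 2.1 records that the sponsor ended the study early and that patients were called in for a last visit.

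**The concern.** The maximum of several readings with error is not an unbiased estimate of the height reached. It selects the reading with the most favourable error, and a later, lower reading cannot correct an over-reading. If baseline is one of the candidates, maximum minus baseline is at least zero for every patient, including one who had already stopped growing. The expected error also grows with the number of readings, which can differ between patients because the study ended early.

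No comparison group is described in which the same artefact would cancel, so it passes directly into the reported mean change. Section 2.3.1 excludes implausible glucose and insulin values, but no corresponding rule is given for height, which is measured by routine practice.

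A second, conditional problem concerns the age limits. If age is taken at the date of the maximum, a small measurement difference can decide whether a fully grown EP00-401 discontinuer is counted. Suppose a woman's highest reading falls at 15.8 years and she measures 0.2 cm less at 20. Her final height is then dated before the limit and she leaves the summary.

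**Working it through.** The SAP gives no figure for this endpoint, so there is nothing to reproduce. The check uses order statistics, confirmed by simulation of 400,000 patients per scenario.

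**Inputs from the SAP**
- Final height is the maximum (2.3.2.2).
- There are up to five scheduled heights: baseline plus follow-up at 6 months, 1, 5 and 10 years (2.3.2.2).
- The summary is the change from baseline (4.7.2.2).

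**Assumptions, not in the SAP**
- Measurement errors are independent and normal, with SD σ of 0.3, 0.5 or 1.0 cm.
- True growth after baseline is either zero or one of two patterns given below.

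**Formula.** For n independent standard normal errors, the expected maximum is e(n) = ∫ x · n · φ(x) · Φ(x)^(n−1) dx. This gives e(1) = 0, e(2) = 0.564, e(3) = 0.846, e(4) = 1.029 and e(5) = 1.163. With k follow-up visits and no growth:
- baseline included: spurious mean gain = σ · e(k+1), and the change is never below zero;
- post-baseline only: spurious mean gain = σ · e(k), and the change is negative with probability 1/(k+1).

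**No true growth, baseline included (cm)**

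| Follow-up visits | σ = 0.3 | σ = 0.5 | σ = 1.0 |
|---|---|---|---|
| 1 | 0.17 | 0.28 | 0.56 |
| 2 | 0.25 | 0.42 | 0.85 |
| 3 | 0.31 | 0.51 | 1.03 |
| 4 | 0.35 | 0.58 | 1.16 |

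For example, four follow-up visits at σ = 0.5 give 0.5 × 1.163 = 0.58 cm. The simulated minimum change was 0.000 in every scenario.

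**No true growth, post-baseline maximum.** The bias is 0, 0.564, 0.846 and 1.029 error SDs with one to four follow-up visits. At σ = 0.5 that is 0, 0.28, 0.42 and 0.51 cm. The change is negative in 50%, 33%, 25% and 20% of patients.

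**Residual growth, baseline included, σ = 0.5.** Bias is measured against the true gain at the last visit attended.
- True cumulative gain of 0.5, 0.8, 1 and 1 cm at the four visits: bias 0.10, 0.18, 0.25 and 0.39 cm.
- True cumulative gain of 1, 2, 3 and 3 cm: bias about 0.03 cm or less at the first three visits, then 0.29 cm at the fourth, where growth has stopped.

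**Comparator.** With no true growth, last height minus baseline has mean change 0 for any number of visits and is negative in about half of patients.

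**SDS.** Baseline height SDS uses the reference for chronological age, whereas final height SDS uses the reference for 18 years or older (5.2). A patient still below that age at baseline is compared with a different reference mean, so the SDS change can be negative even when the cm change is not. The cm bias still enters the numerator.

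**The case against.** The strongest objection is that the defining sentence does not say baseline is included. That comes from the sentence before it, on when height is measured, and the objective in section 2.2 speaks of final height during follow-up. This stands, and it makes the claim that the change can never be negative conditional. It does not remove the bias, which returns from the second follow-up visit on.

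On the age limits, the wording can equally mean the patient's age when final height is evaluated. The woman in the example would then be kept. Her exclusion follows from one reading only, and the limits concern EP00-401 discontinuers alone.

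A reader might also infer that the artefact makes up a large share of the reported gain. The documents do not support that. They give neither the measurement error nor the remaining growth after baseline, and under the faster assumed growth the bias is about 0.03 cm until growth stops. Patients who discontinued EP00-401 early may have had appreciable growth left.

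Nor is any between-group comparison distorted: no comparator is described, no subgroup analysis is planned and all summaries are descriptive. Observed height at each visit is also tabulated, so readers will see last-visit height, although not its change from baseline.

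Finally, height does not normally fall in adolescence, so the maximum does guard against a low last reading. That is a real advantage, but it is bought with an error that always runs in one direction.

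**Conclusion.** The concern holds in a limited form. Taking the maximum biases the mean change in final height upward. The size depends on an error SD that the SAP does not give:
- about 0.2 to 0.6 cm at 0.3 to 0.5 cm without growth and with baseline included;
- about 0.03 to 0.4 cm at 0.5 cm under the two assumed growth patterns.

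The increase with visit number is clear once growth has stopped. That the change cannot be negative applies to cm only, and only if baseline is in the maximum; it should not be extended to final height SDS. Possible exclusion of a fully grown discontinuer is an ambiguity to close, not an established consequence. This is a worthwhile, inexpensive improvement to a secondary descriptive endpoint. It does not threaten any conclusion that the plan tests.

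**What to change.** In sections 2.3.2.2 and 4.7.2.2:
- define final height as the last available post-baseline height;
- for patients who discontinued EP00-401, apply the SAP's existing age limits at the date of that measurement;
- take final height SDS from the same measurement, with the reference already set in section 5.2;
- keep the maximum as a sensitivity listing that flags patients whose maximum exceeds their last value.

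The cost is a wording change and one derivation, using heights already collected. The downside is that an erroneously low last reading is no longer masked by an earlier, higher one; the flagged listing makes such cases visible. A patient with no post-baseline height, which section 2.6 allows when only an adverse event is documented, would have no final height, and the number of such patients should be reported.

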2.4 Statistical methods planned in the protocol

Planned analyses are described in Section 10 of the protocol. Safety and efficacy endpoints will be summarized descriptively.

2.5 Determination of sample size

All patients who participated in the EP00-401 study and received at least one dose of study medication are intended to enter the observational period.

2.6 Definitions of analysis sets

The **safety population** (SAF) comprises all who enter the observational period i.e. at least one visit date additional to visit F0 or an adverse event starting or worsening on or after baseline have to be documented. The SAF population will be the basis for all safety analyses.

The **full analysis set** (FAS) population comprises all patients who received at least one dose of study medication, as defined for the final analysis of study EP00-401. All baseline and efficacy analyses will be summarized for the FAS. Only patients from SAF will be included.

